### **3.4. Breaking the Blind**

The Sponsor designee (eg, IRT vendor, etc.) will have a designated randomization administrator who will maintain the randomization codes in accordance with Standard Operating Procedures to ensure that the blind is properly maintained and that only Sponsor personnel who require knowledge of treatment assignments will be unblinded (eg, staff involved in maintaining the randomization codes or serious adverse events [SAEs] reporting).

Unblinding should only occur in the event of an emergency or adverse event for which it is necessary to know the study drug treatment to determine an appropriate course of therapy. If the patient's study drug must be unblinded, the Investigator or qualified designee should contact IRT, but not the site's unblinded pharmacist, for the study drug information. The IRT documentation indicating the blind break must be retained with the patient's source documentation in a way as to not unblind the treatment assignment to other site or Sponsor personnel.

If possible, the Investigator should attempt to contact the site monitor or the Medical Monitor prior to unblinding in order to get additional information about the study drug. If not possible, the Investigator should notify the site monitor or Medical Monitor as soon as possible of the unblinding without disclosing the treatment assignment of the unblinded patient. The Investigator must document the patient's identification, reason for breaking the blind, and the date and time for breaking the blind.

After the database is locked and the SAP is final, the study blind codes will be broken.

### **3.5. Study Assessments**

Table 1 presents the schedule of procedures of the study.

**Table 1. Schedule of Procedures**

Procedure	Screening		Treatment							TOC	LFU
	-48 Hours to Day 1 [1]	Day 1	Day 2 [2]	Day 3 [2]	Day 4 [2]	Day 5 [2]	Day 6 [2]	Day 7 to Day 14/ EOT +1 Day [2]	7 Days Post-EOT ±1 Day [3]	7 Days Post-TOC ±2 Days [3]	
Informed consent	X										
Inclusion/exclusion criteria	X										
Medical/surgical history	X [4]										
Prior/concomitant medications	X [5]	X	X	X	X	X	X	X	X	X	
Demographics [6]	X										
Complete physical examination [7]	X		X	X	X	X	X	X [8]			
Limited physical examination [7]			X	X	X	X	X		X	X	
Vital signs [9]	X	X	X	X	X	X	X	X	X	X	
Assess clinical signs/symptoms	X	X	X	X	X	X	X	X	X	X	
Assess clinical outcome [10]								X [11]	X [10]	X [10]	
Randomization		X									
Pregnancy test [12]	X							X [13]			
Serum chemistry [14]	X	X		X		X		X [11]	X	X	
Hematology [15]	X	X		X		X		X [11]	X	X	
Urinalysis [16, 17]	X	X		X		X		X [11]	X	X	
12-lead ECG	X [18,19]				X [18]						
Blood cultures		X [20]	X [20]	X [20]	X [20]	X [20]	X [20]	X [20]	X [20]	X [20]	
Urine cultures	X [21,22]					X [21]		X [21]	X [21]	X [21]	
Administer study drug [23]		X	X	X	X	X	X	X			
Administer imipenem/cilastatin [24]		X	X	X	X	X	X	X			
Assessment of adverse events [25]	X	X	X	X	X	X	X	X	X	X	
PK samples		X [26]			X [26]						

- Screening procedures may be performed up to 48 hours prior to the first dose of study drug. All Screening procedures must be completed prior to randomization and the first dose of study drug (Day 1). All Screening laboratories will be performed at the local laboratory and may have been collected as standard of care within 48 hours prior to randomization, with the exception of serum creatinine determination, which must be obtained at the local laboratory within 24 hours of the first dose of study drug.
- Study procedures are only required on treatment days that the patient receives IV therapy. If EOT occurs before Day 14, study procedures are not required to be performed on subsequent days until the TOC Visit.
- The TOC Visit must occur 7 days (±1 day) after the EOT Visit. The LFU Visit must occur 7 days (±2 days) following the TOC Visit. The LFU Visit should be performed as an in-office visit; however, if the patient is unable to attend the LFU Visit at the site, then the patient may be contacted by telephone call for follow-up assessment of concomitant medications, clinical signs and symptoms, and adverse events.
- Obtain medical/surgical history, including urological history; record inactive conditions diagnosed within the previous 5 years, complete urological/renal history, and all active conditions.
- Reasonable effort will be made to determine all relevant treatments (including all antibiotics, prescription and non-prescription medications, herbal medications, and vitamin supplements, supportive therapies, and non-pharmacologic treatments) received within 14 days before the first dose of study drug and during the study.
- Demographic data will be collected, including sex, age, race, and ethnicity.
- Complete physical examination includes weight (and height at Screening only). Limited physical examination does not include weight.

8. A complete physical examination is required on Day 7 and at the EOT Visit only. A limited physical examination should be performed on Day 8 to Day 14 if the patient has received blinded study drug.
9. Vital signs include blood pressure, heart rate, and respiratory rate.
10. If a patient is a clinical failure at EOT, the patient is automatically considered a failure at the TOC and LFU Visits, and the assessment of clinical response by the Investigator should be listed as "failure at EOT."
11. Day 7 and EOT Visit only.
12. A highly sensitive urine or serum pregnancy test will be performed at Screening, before the first dose of study drug, and at EOT for women of childbearing potential. If Screening occurs within 48 hours of randomization, study procedures performed at Screening do not need to be repeated.
13. EOT Visit only.
14. See Protocol Appendix B for a full list of clinical laboratory analytes.
15. Hematology includes complete blood count (with red blood cell count, total white blood cell count with differential counts, platelet count, hemoglobin, and hematocrit). See Protocol Appendix B for a full list of clinical laboratory analytes.
16. Urinalysis includes urine dipstick analysis for leukocytes, nitrites, or a catalase test of the urine specimen, microscopic evaluation, specific gravity, and pH. See Protocol Appendix B for a full list of clinical laboratory analytes.
17. Urine sample should be collected by clean-catch midstream or other appropriate method that minimizes risk of bacterial contamination.
18. The 12-lead ECG will be performed at baseline at Screening and repeated as close as possible to the end of the infusion of study drug administration on the day on which post-dose PK samples are drawn (Day 3, Day 4, or Day 5). The day on which the post-dose PK samples are drawn is at the discretion of the Investigator. All 12-lead ECGs will be performed after the patient has been in a supine position for at least 10 minutes.
19. Consult the Medical Monitor and local cardiologist in cases of clinically significant abnormal findings (eg, a QTcF >480 msec).
20. If baseline blood cultures were positive, repeat blood cultures should be obtained daily until negative or if the patient is a treatment failure.
21. An adequate clean-catch urine specimen for culture (or other appropriate method to collect a urine culture that minimizes risk of bacterial contamination) should be obtained at the specified time points. At any point in the study, if a patient fails while on therapy, a urine specimen should be obtained.
22. A repeat urine sample for culture must be obtained prior to the start of study drug treatment for any patient enrolled in the study who has received a single dose of a short-acting antibiotic in the 24 hours prior to randomization or for patients who failed preceding antimicrobial therapy. This sample should be taken as close to randomization as possible (within 2 hours prior to randomization, if possible).
23. Study drug should be administered q6h for a minimum of 7 days (28 doses), as described in the protocol.
24. All patients will be administered impipenem/cilastatin q6h.
25. Adverse events should be captured as described in the protocol.
26. PK samples will be collected immediately prior to the first dose of study drug on Day 1 and post-dose of any study drug infusion on Day 4 ( $\pm 1$  day) at the end of the infusion when the infusion pump is turned off, 0.5 hours after the end of the infusion, 2 hours after the end of the infusion, and 3 hours after the end of the infusion (prior to the start of the next infusion).

ECG = electrocardiogram; EOT = End of Treatment; IV = intravenous; LFU = Late Follow-up; PK = pharmacokinetics; q6h = every 6 hours; QTcF = QT interval corrected using Fridericia's formula; TOC = Test-of-Cure.

#### **4. SAMPLE SIZE DETERMINATION**

Overall, the study is anticipated to randomize approximately 80 patients in a 2:1 ratio to receive ETX2514SUL or placebo. No formal power calculations have been performed for this study. The sample size is based on practical considerations.

#### **5. STUDY ASSESSMENT**

##### **5.1.1. Assessment of Clinical Signs and Symptoms**

Clinical signs and symptoms will be assessed at Screening, daily during IV treatment beginning on Day 2, at the EOT Visit, at the TOC Visit, and at the LFU Visit. When possible, the same study personnel should complete the assessments at approximately the same time each day. Maximum daily temperature (defined as the maximum temperature reported on a single calendar day) will be recorded. Body temperature may be taken per the site's preferred method and will be recorded in the appropriate eCRF. The same method of measuring a patient's body temperature should be used throughout the study.

The following signs and symptoms will be assigned a classification of absent, mild, moderate, or severe:

- Urinary frequency,
- Urinary urgency,
- Dysuria,
- Nausea,
- Vomiting,
- Abdominal pain,
- Suprapubic pain or discomfort,
- Flank pain, and
- Costo-vertebral angle tenderness.

##### **5.1.2. Clinical Outcome**

Based on the assessment of signs and symptoms, the Investigator will choose 1 of the following clinical outcomes at the Day 5, EOT, and TOC Visits:

Clinical cure: complete resolution or significant improvement of signs and symptoms of cUTI or AP that were present at baseline and no new symptoms, such that no further antimicrobial therapy is warranted.

Clinical failure: symptoms of cUTI or AP present at study entry have not significantly improved or completely resolved, or new symptoms of cUTI or AP have developed and require the initiation of a non-study antibacterial drug therapy, or death.

Clinical indeterminate: insufficient data are available to determine if the patient is a cure or failure.

Based on the assessment of signs and symptoms, the Investigator will choose 1 of the following clinical outcomes at the LFU Visit:

Sustained clinical cure: met criteria for clinical cure at the TOC Visit and the LFU Visit.

Relapse: clinical cure at the TOC Visit but signs and symptoms of cUTI or AP are present at the LFU Visit.

Clinical failure: clinical failure at the TOC Visit carried forward to the LFU Visit or death between the TOC Visit and LFU Visit.

Clinical indeterminate: insufficient data are available to determine if the patient is a sustained clinical cure or clinical relapse.

Note: if a patient is a clinical failure at EOT, the patient is automatically considered a failure at the TOC and LFU Visits, and an assessment of clinical response by the Investigator will be listed as “failure at EOT.”

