#### **5.1.4. Microbiologic Outcome**

##### **5.1.4.1. Per-Pathogen Microbiologic Outcome**

Microbiologic outcome at Day 5, EOT, and TOC will be programmatically determined for each pathogen isolated at baseline. Per-pathogen microbiological response categories are eradication, persistence, and indeterminate defined as following:

Microbiologic eradication: the demonstration that the baseline bacterial pathogen(s) is reduced to  $< 10^4$  CFU/mL according to the Food and Drug Administration (FDA) criteria and  $< 10^3$  CFU/mL according to the European Medicines Agency (EMA) criteria on urine culture and negative on repeat blood culture (if positive at baseline).

Microbiologic persistence: the urine culture grows  $\geq 10^4$  CFU/mL for the FDA ( $\geq 10^3$  CFU/mL for the EMA) of any of the baseline pathogen(s) identified at study entry and/or a blood culture demonstrates the same baseline pathogen(s). Patients who are a persistence at EOT will be considered a persistence at TOC.

Microbiologic indeterminate: no follow-up urine culture is available, or the follow-up urine culture cannot be interpreted for any reason, or the follow-up urine culture is considered contaminated. For a baseline blood pathogen, no follow-up blood culture is available.

A per-pathogen microbiological outcome will be determined at the LFU visit. Per-pathogen microbiological outcome categories are sustained eradication, presumed sustained eradication,

continued persistence, recurrence, and indeterminate. A per-pathogen microbiologic outcome of persistence at TOC will be considered a continued persistence at LFU defined as following:

Sustained microbiologic eradication: microbiologic eradication at the TOC Visit and the LFU Visit.

Presumed sustained microbiologic eradication: no urine culture was done at LFU and patient meets clinical criteria for sustained clinical cure.

Microbiologic continued persistence: a per-pathogen microbiologic outcome of persistence at the TOC Visit will be considered a continued persistence.

Microbiologic recurrence: urine culture grows  $\geq 10^4$  CFU/mL for the FDA ( $\geq 10^3$  CFU/mL for the EMA) of any of the baseline pathogen(s) identified at study entry and/or a positive blood culture at any time after documented eradication at the TOC Visit up to and including the LFU Visit.

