## **8.2. Handling of Dropouts/Missing data**

For the primary efficacy outcome measure of overall response, patients with missing data or who are lost to follow-up will be considered as an indeterminate response and are included in the denominator for the calculation of overall success rate. Thus, patients with an indeterminate outcome are considered as failures for the primary analysis. A clinical failure occurring at an earlier time point will be carried forward to the subsequent visits.

In cases of missing or incomplete dates (e.g. AE and concomitant medications), the missing component(s) will be assumed as the most conservative value possible. For example, AEs with missing start dates, but with stop dates either overlapping into the treatment period or missing, will be counted as treatment-emergent, taking the worst-case approach. When partial dates are present in the data, both a partial start date and/or a partial stop date will be evaluated to determine whether it can be conclusively established that the AE started prior to the start of study drug or ended prior to the start of study drug. If the above cannot be conclusively established based on the partial and/or present dates, then the AE will be considered as treatment-emergent. Actual data values as they appear in the original eCRF will be presented in the data listings.

Missing values for other variables will not be imputed and only observed values will be used in data analyses and summaries.

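### The LFU clinical categories do not capture a relapse treated between TOC and LFU, so such a patient can be counted as a sustained clinical cure or may fit no category

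*SAP*

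**What the plan says.** SAP 5.1.2, with the same text in Protocol 7.6 and the synopsis, offers the investigator four clinical outcomes at LFU:

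- One is tied to what is found on the LFU day itself: "Relapse: clinical cure at the TOC Visit but signs and symptoms of cUTI or AP are present at the LFU Visit".
- The favourable outcome rests on two visit days and sets no condition on the time between them: "Sustained clinical cure: met criteria for clinical cure at the TOC Visit and the LFU Visit".
- The unfavourable outcome is limited to a failure already declared by TOC, or a later death.
- The last is indeterminate, for insufficient data.

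The cure criteria, to be met again at LFU, ask for symptoms that are gone or much improved, with nothing new, "such that no further antimicrobial therapy is warranted". At Day 5, EOT and TOC, but not at LFU, failure also covers the case where "new symptoms of cUTI or AP have developed and require the initiation of a non-study antibacterial drug therapy, or death".

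Two other rules bear on the point. SAP 5.1.4.1 words microbiologic recurrence over an interval: "at any time after documented eradication at the TOC Visit up to and including the LFU Visit". SAP 8.2 adds: "A clinical failure occurring at an earlier time point will be carried forward to the subsequent visits".

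LFU falls 7 days (±2) after TOC and may be done by telephone, in which case concomitant medications, symptoms and adverse events are still asked about (Protocol 6.5; SAP Table 1 notes). Sustained clinical cure at LFU is an exploratory endpoint in the MITT, m-MITT, CE and ME Populations (SAP 6.3). A patient with no LFU urine culture who is a sustained clinical cure is scored as presumed sustained eradication (SAP 5.1.4.1). The per-patient rule counts that as sustained eradication (SAP 5.1.4.2).

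**The concern.** An endpoint called sustained cure should fail when the infection comes back and has to be treated. Here the clinical definition takes two snapshots and ignores the days between them. New symptoms needing a non-study antibacterial make a patient a failure up to TOC, but after TOC no category mentions that event. The microbiologic counterpart is worded over the interval; the clinical one is not.

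Sustained clinical cure is the plan's only responder endpoint for clinical durability. Relapses prompt enough to be treated and cleared before LFU are the ones the wording can miss. With a telephone LFU, one such patient can be a success on both the clinical and the microbiologic endpoint.

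**Working it through.** The plan has no figure to reproduce: the sample size rests on practical grounds and no rates are given. The check is to run a patient through the LFU categories and then size one misclassification.

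**Case A: cured at TOC, relapsed, non-study course completed, symptom-free at LFU.**
- Relapse: not met, since nothing is present at LFU.
- Failure: not met, since there was no TOC failure and no death.
- Indeterminate: not met, since the data are sufficient.
- Sustained cure: met on the literal wording, since the criteria hold at both visits.

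**Case B: same patient, still on the non-study antibacterial at LFU.**
- Relapse, failure and indeterminate: not met, as in Case A.
- Sustained cure: can fail, because further therapy is arguably still warranted. If it fails, no category is left.

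**Case C: the investigator regards the interval episode as a clinical failure.** SAP 8.2 would carry it to LFU. The LFU failure definition in SAP 5.1.2 admits only failure at TOC or death, so the two sections disagree.

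**Which case applies depends on timing.** LFU falls between TOC + 5 and TOC + 9 days (7 − 2 and 7 + 2). If treatment starts on day s after TOC and lasts L days, its last day is s + L − 1. It is over before LFU when s + L is no greater than the LFU day. For illustration, with s = 2:
- L = 3 ends on TOC + 4, before every permitted LFU day (Case A).
- L = 7, the length of the trial's own standard course, ends on TOC + 8. Only an LFU on TOC + 9 follows it; on earlier days Case B applies.

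**A related overlap.** Cure allows improvement short of full resolution. A patient with unchanged mild residual symptoms at TOC and LFU can meet both sustained cure and relapse as worded.

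**Size of one misclassification.** 80 patients at 2:1 gives 80 × 2/3 ≈ 53 and 80 × 1/3 ≈ 27. Assuming all 80 are in the MITT Population:
- ETX2514SUL: 1/53 = 1.9 points per patient.
- Placebo: 1/27 = 3.7 points per patient; two patients, 2/27 = 7.4 points.

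**Against the precision available.** The continuity-corrected half-width is 1.96 × √[p1(1 − p1)/53 + p2(1 − p2)/27] + (1/53 + 1/27)/2. Using an unpooled standard error and assumed sustained-cure rates in both arms:

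| Assumed rate | Counts | 95% CI for difference (points) | Half-width |
|---|---|---|---|
| 80% | 42/53, 22/27 | −23.3 to 18.8 | 21 |
| 85% | 45/53, 23/27 | −19.6 to 19.0 | 19 |
| 90% | 48/53, 24/27 | −15.3 to 18.7 | 17 |

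The total overstatement in an arm would be (TOC cure rate) × (share of cures relapsing before LFU) × (share of those scored as sustained cure). None of the three is in the documents, so no total is given.

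**The case against.** A reader might infer that every treated relapse between TOC and LFU is scored as a sustained cure. The documents do not support that.

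- The cure criteria apply again at LFU. With only 5 to 9 days available, many patients could still be on treatment and fail the therapy clause. This stands, but it leads to Case B, where the patient has no category, and not to a correct one.
- The investigator chooses the clinical outcome; it is not programmed. The absence of new symptoms is not expressly limited to the visit day, so an investigator aware of the episode might decline to call it a cure. This stands too. It means that two investigators may classify the same patient differently.
- SAP 8.2 supports treating the episode as a failure. However, failure by new symptoms and non-study therapy is defined only for visits up to TOC, and the LFU failure definition does not admit a later one. SAP 8.2 is a competing reading, not a resolution.
- Protocol 4.3 permits withdrawal when prohibited medication is required, and Protocol 6.6 then has the next visit completed at termination. Some relapses would thus be assessed while symptomatic and counted correctly. Withdrawal is optional, so this helps only in part.
- A positive culture taken during the episode could count as microbiologic recurrence. No culture is scheduled between TOC and LFU, so this depends on local practice.
- SAP 8.11.4, on the exploratory endpoints, is redacted and may hold a further rule. That cannot be excluded. The definitions in SAP 5.1.2 are fully visible and are the ones an investigator would apply.
- The episode need not vanish from the report: adverse events are tabulated and listed, and medications are summarised and listed by patient. It can still be missing from the endpoint.

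**Conclusion.** The point holds in limited form. The LFU categories do not say how to classify a relapse treated between TOC and LFU. On the literal wording, a patient who has finished treatment and is symptom-free can be a sustained clinical cure, and a patient still on treatment may fit nowhere. SAP 5.1.2 and SAP 8.2 also disagree on whether a post-TOC failure can be carried to LFU.

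The reach is limited to the exploratory LFU endpoints: sustained clinical cure and, when no LFU culture is done, sustained eradication. The primary and secondary efficacy endpoints are at TOC and are untouched. The primary objective is safety, and efficacy is descriptive.

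A reader might also infer a definite overstatement of durability, or a definite narrowing of the difference between arms. Neither can be established: the documents give no relapse rate, no share treated and resolved by LFU, and nothing on whether that share would be alike in the two arms. What can be said is that one patient moves an arm by 1.9 or 3.7 points if all 80 are in the MITT Population. Interval half-widths are about 17 to 21 points under assumed rates of 80% to 90%.

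**What to change.** For outcome scoring only, and before the blind is broken, revise relapse in SAP 5.1.2, Protocol 7.6 and the synopsis along these lines:

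*Relapse: clinical cure at TOC followed, at any time after TOC up to and including the LFU Visit, by (a) return, worsening or new onset of signs or symptoms of cUTI or AP for which a non-study systemic antibacterial was started, or (b) return, worsening or new onset of signs or symptoms of cUTI or AP present at the LFU Visit.*

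Then:

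- State that a patient meeting (a) or (b) cannot be a sustained clinical cure or a presumed sustained eradication. Without an LFU culture, such a patient falls under the existing microbiologic indeterminate category unless recurrence was documented.
- Derive (a) from the antibacterial's start date and indication, which Protocol 5.5.3 already requires.
- Reconcile the LFU failure definition in SAP 5.1.2 with the carry-forward sentence in SAP 8.2, and check both against SAP 8.11.4.

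Limb (b) also removes the overlap for unchanged residual symptoms. The cost is one revised definition, a short scoring statement and one programmed check on existing data; nothing changes for patients. The downside is a slightly lower sustained-cure rate.
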